4.7 Follow-Up

The patients will be followed for 48 hours post-procedure or hospital discharge, whichever occurs first. No additional patient contact is required for this study. Data collection must be completed on all subjects before they are discharged from the hospital.

4.8 Schedule of Data Collection

Data collected for all subjects enrolled in this study are listed in the following Schedule of Activities (Table 1), many of which are part of routine data collection for all PCI procedures:

Table 1: Schedule of Activities

	Pre-procedure	Procedure	Post Procedure
Patient Eligibility Criteria ¹	X		
Medical history ¹	X		
Clinical assessment & Physical exam	X ¹		X
Non-Cardiac Laboratory Tests	X ¹		X
Cardiac enzymes	X ²		X ³
12-lead ECG			X ⁴
Angiography		X	
Procedure Parameters (procedure time, fluoroscopy time, etc.)		X	
Contrast volume		X	
Record of SAEs		X	X
Data for lesion classification		X	

¹ Within 30 days of index procedure.

² Pre-procedure cardiac enzymes within 7 days of index procedure, if collected.

³ Post-procedure cardiac enzyme collection is left to the discretion of the investigator and shall be dictated by the patient's clinical symptoms.

⁴ Post-procedure 12-lead ECG: it is recommended that an ECG be performed at the time of discharge but is not required for the protocol.

5.0 Data Collection

5.1 Study Data Requirements

CRFs received from the clinical site will be documented with their date of receipt and entered into the trial database. A database that is compliant with 21 CFR Part 11. If there is missing,

incomplete, unclear or discrepant information recorded on a CRF, a Data Clarification Form (DCF) will be generated. The DCF will be sent to the Investigator for completion and signed by the appropriate site personnel. The DCF will then be sent back to Corindus to update the data-base.

6.0 Monitoring Procedures

6.1 Investigator/Site Selection

The minimum criteria for selecting a Clinical Investigator/site will include the following:

- Education, experience and interest of the Investigator;
- Expertise in the area of interest;
- Adequacy of resources, facilities and equipment at the investigational center;
- Ability of the Investigator and center to meet activation requirements in a timely manner;
- Patient population of the center and the ability to enroll adequate numbers of subjects;
- Status with regulatory agencies;
- Investigator performance in previous clinical trials;
- Investigator participation in concurrent studies; and
- No known financial conflicts of interest.

6.2 Site Initiation

The following documents must be received prior to clinical trial site initiation/activation and maintained at the site and Corindus, if applicable:

- Signed Clinical Trial Agreement;
- Current Curriculum Vitae (CV) for Primary Investigator(s);
- Corindus and EC approved Informed Consent Form; and
- EC Approval Letter.

Additional items that may be collected prior to activation, but not required at that time:

- Investigator Financial Disclosure Form(s);
- EC Membership List and/or Accreditation Statement; and
- Site Personnel Training Record(s)

6.3 Case Report Form Review

CRFs received from the clinical site will be documented with their date of receipt and entered into the trial database. If there is missing, incomplete, unclear or discrepant information recorded on a CRF, a Data Clarification Form (DCF) will be generated. The DCF will be sent to the Investigator for completion and signed by the appropriate site personnel. The DCF will then be sent back to Corindus to update the database.

6.4 On-site Monitoring

The Clinical Representative will maintain personal contact with the Investigator and staff by fax, phone, mail, and on-site visits. The monitor will require access to all subjects' records at. These may include:

- Clinic charts
- Hospital charts
- Angiograms
- Investigator Administrative Records
- Subject Binders

Monitoring will verify:

- Written informed consent has been obtained for each subject;
- Device Accountability;
- Continued plan and regulatory compliance; and
- Verification of data recorded on Case Report Forms to source documents.

6.5 Final Monitoring Visit

At the close of the trial, the Clinical Representative will make a final on-site visit. The purpose of this visit is to:

- Collect all outstanding study data;
- Insure that the Investigator's files are accurate and complete;
- Review record retention requirements with the Investigator; and
- Assure that all requirements are met for the closure of the study.

6.6 Confidentiality and Protection of Study Files

In conducting the study, the investigational site will comply with all applicable federal and regional laws and regulations relating to the confidentiality and security of individually identifiable medical information.

If a subject revokes authorization to collect or use PHI, the Investigator, by regulation, retains the ability to use all information collected prior to the revocation of subject authorization. For subjects that have revoked authorization to collect or use PHI, attempts should be made to obtain permission to collect at least vital status (i.e. that the subject is alive) at the end of their scheduled study period.

In accordance with PHI regulations, subject records leaving the facility for purposes of the investigation should be identified by the Subject ID assigned for the study, and should not include the subject's name, whenever practical. Every effort should be made to "black out" subject's name from medical records including films prior to sending to Corindus or the core lab.

All personal information pertaining to subjects will be kept confidential. This study is being conducted in compliance with FDA 21 CFR. Whenever practical, subjects will be identified only by their Subject ID Number and initials. Clinical trial documents and hospital and clinic medical records pertaining to study subjects may be reviewed by Corindus study personnel or their representatives, FDA, or other health inspectors as needed to assure compliance with all study requirements.

Information obtained during executing this study, including still and motion photography, may be presented for regulatory, clinical or educational purposes as long as no subject is identified.

The data collected is the property of Corindus.

7.0 Data Quality Assurance

7.1 Clinical Event Handling

This study will collect data on subjects undergoing standard treatments and procedures. The site will be asked to provide documentation of events on the paper CRFs related to specific procedural events and device complications. The Sponsor will identify events associated with the study endpoints and additional event review may be performed, as described below. The site will follow their routine hospital procedures for adverse event handling, as necessary.

7.2 Study Endpoint Event Adjudication

A site independent review of all clinical events associated with the study endpoints will be conducted. Adjudication will be based on narratives and source data supplied by the site. Source data that may be collected for review include, but are not limited to, de-identified angiograms (diagnostic and procedural), catheterization lab report, procedure report, discharge summary, lab reports, and pre- and post-procedure ECGs. The site may be contacted for queries and additional support documentation.

8.0 Statistical Methods

This is a prospective, single-arm, single center, non-randomized feasibility study of the CorPath POP System designed to evaluate the safety and effectiveness of the clinical and technical performance of the CorPath GRX POP System in the REMOTE delivery and manipulation of coronary guidewires and stent/balloon catheters, and remote manipulation of guide catheters for use in PCI. The detailed investigational plan, pre-defined nature of study endpoints, and prospective nature of data collection help provide protection against study bias. The intent of this study is to gather preliminary data of performance and does not have powered pre-specified pass/fail objectives and associated type I error rates. As such, interim analyses may be performed on accruing data during the study.

The sample size of up to 5 subjects will provide a reasonable degree of precision for events that occur during the study. For example, at an assumed success rate of 99%, the expected confidence interval width for the success rate based on a two-sided 95% exact binomial confidence interval will be less than 19%. Similarly, at an assumed safety outcome rate of 1%, the expected confidence interval width for the success rate based on a two-sided 95% exact binomial confidence interval will be less than 19%.

Corindus' standard operating procedures for study monitoring, data editing, data management, computer entry and verification of database accuracy will be implemented prior to study onset. After verification of database accuracy and closure, an examination of the distribution of each numeric variable (i.e. study endpoint) will be performed. Descriptive statistics for each variable will be calculated which will include measures of central tendency, variation, a frequency histogram and a count of the number of missing values.

When the arithmetic mean is found not to be an appropriate measure of central tendency, alternative statistics will be considered (e.g. median). When the distribution of a variable does not support the use of parametric statistics, nonparametric approaches or data transformations may be implemented. Two-sided 95% confidence intervals will be used for means or proportions as appropriate for primary and secondary outcome measures. For proportions, exact binomial confidence intervals will be used. If data transformations are used, they will be specified in the final clinical report.

It is not a planned part of this study to utilize data imputation for missing values. However, should data imputation be used at the time of analysis, the method will be specified in the final clinical report. Exploratory analyses may be performed to better characterize and understand the data.

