Date

Sponsor Summary

Sponsor:	Corindus Vascular Robotics, Inc.
Address:	[name]
Phone Numbers:	[contact]
Primary Contact:	[name], BS
Email:	[contact]
Principal Investigator:	[name], M.D. [name]
Monitoring:	Corindus Vascular Robotics, Inc. [name]
Study Product:	CorPath®GRX + ReMOTE Proof of Principle (POP) System
Protocol Number:	2018-001

GRX with ReMOTE Proof of Principle (POP) Study Summary

Title:	CorPath GRX with ReMOTE Proof of Principle (POP): First in Human
Short Title:	GRX with ReMOTE: First in Human
Device:	
CorPath®GRX + ReMOTE Proof of Principle System (CorPath GRX POP System) consists of:
 
 • CorPath GRX Bedside Unit (Extended Reach Arm, Robotic Drive and single-use Cassette) • Local and Remote Control Station
Regulatory Status:	
The CorPath GRX System (Bedside Unit and Remote Work-space) was granted CM Mark approval on February 29, 2016 and was granted US Food and Drug Administration on October 27, 2016.
 
The Local and Remote Control Station is a validated working prototype.

Indication for Use:	
The CorPath GRX System is intended for use in the remote delivery and manipulation of coronary guidewires, rapid exchange balloon/stent catheters and remote manipulation of guide catheters during percutaneous coronary interventional (PCI) procedures.

Study Objective:	
To evaluate the safety and performance of CorPath GRX POP System, in the ReMOTE (location outside hospital) delivery and manipulation of coronary guidewires and stent/balloon catheters, and manipulation of guide catheters during PCI procedures.

Study Design:	
Prospective, single-arm, single center, non-randomized feasibility study of the CorPath GRX POP System to examine its performance during remote angioplasty (ballooning) and stenting and patient outcomes through 48 hours post-PCI procedure hospital discharge, whichever occurs first.

Principal Investigator:	[name].
Sample Size:	Up to 5 subjects shall be treated in the study.
Investigational Sites:	One (1) international OUS investigative site will participate in this study.
Study Duration/ Follow-up Period:	The anticipated enrollment period is one (1) month. All subjects will be followed post ReMOTE CorPath PCI through 48 hours post-procedure or hospital discharge, whichever occurs first.

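### With 5 subjects the expected exact 95% interval is about 53 points wide, not under 19 as Section 8.0 states; even a perfect result gives 52 points

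*Combined protocol and SAP*

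**What the plan says.** The Study Summary sets the sample size: "Up to 5 subjects shall be treated in the study". Section 4.1 gives the same cap. Section 8.0 then offers a precision argument for it: "The sample size of up to 5 subjects will provide a reasonable degree of precision for events that occur during the study".

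Two examples support that sentence. The first, "at an assumed success rate of 99"%, concludes that "the expected confidence interval width for the success rate based on a two-sided 95% exact binomial confidence interval will be less than 19"%. The second begins "Similarly, at an assumed safety outcome rate of 1"% and gives the same limit, again describing it as a width for the success rate.

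Section 8.0 also fixes the analysis method: "For proportions, exact binomial confidence intervals will be used". It states that the study collects preliminary data and has no powered pass/fail objectives.

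**The concern.** An exact 95% interval from five binary observations is very wide whatever the result, so a width under 19 points looks impossible on its face. All the inputs needed to check it are in the text: n, the assumed rates, the confidence level, the sidedness and the interval method.

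In a study with no hypothesis test, interval width is the whole statistical content of the sample-size rationale. The two examples correspond to the two primary endpoints: device technical success (Section 3.2.1) and in-hospital MACE (Section 3.2.2). This is first-in-human use of a prototype remote control station, and the ethics committee reviews this protocol (Section 9.1). With zero events the interval's width equals its upper limit. There is therefore a real risk that 0/5 MACE is read as excluding rates above about 19%, when the data would remain compatible with rates up to 52.2%. At the plan's own 1% assumption, 0/5 has probability 0.99^5 = 0.951, so the misreading concerns the most likely result.

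**Working it through.** **Inputs, all from Section 8.0:** n = 5 at most; assumed rates 0.99 (success) and 0.01 (safety outcome); two-sided 95%; exact binomial. Section 3.2 allows lesion-based parameters, but Section 4.5 admits a single study lesion per subject, so n stays at 5.

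**Step 1. Exact interval for each possible result.** For x = n the Clopper-Pearson lower limit solves p^n = 0.025 and the upper limit is 1. At n = 5 the lower limit is 0.025^(1/5) = 0.4782, so the width is 1 − 0.4782 = 0.5218. The case x = 0 is the mirror image. The other limits come from beta quantiles.

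| Successes out of 5 | 95% exact interval | Width (points) |
|---|---|---|
| 5 | 47.8% to 100% | 52.2 |
| 4 | 28.4% to 99.5% | 71.1 |
| 3 | 14.7% to 94.7% | 80.1 |
| 2 | 5.3% to 85.3% | 80.1 |
| 1 | 0.5% to 71.6% | 71.1 |
| 0 | 0% to 52.2% | 52.2 |

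No result comes within 33 points of the stated limit (52.2 − 19 = 33.2).

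**Step 2. Expected width, the quantity the plan names.** This is the sum over x of the Binomial(5, p) probability times width(x). At p = 0.99:

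- x = 5: 0.99^5 × 0.5218 = 0.9510 × 0.5218 = 0.4962
- x = 4: 5 × 0.99^4 × 0.01 × 0.7114 = 0.0480 × 0.7114 = 0.0342
- x = 3: 10 × 0.99^3 × 0.01^2 × 0.8006 = 0.00097 × 0.8006 = 0.0008
- x ≤ 2: negligible

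The total is 0.531, or 53.1 points. By symmetry p = 0.01 gives the same value. The ratio to the stated limit is 53.1/19 = 2.80; for the narrowest interval it is 52.2/19 = 2.75.

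**Step 3. Fewer subjects.** Since 5 is a maximum, smaller n must be considered. The expected width is 61.0 points at n = 4 and 71.3 at n = 3.

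**Step 4. Sample size at which the figure would be true.** The expected exact width at p = 0.99 is 19.2 points at n = 19 and 18.4 at n = 20. It first falls below 19 at n = 20.

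**Step 5. Other readings at n = 5.**

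| Reading | Value (points) |
|---|---|
| Half-width of the narrowest exact interval | 26.1 |
| One-sided 95% exact bound with 0/5, distance from zero | 45.1 |
| Expected mid-P width | 46.1 |
| Expected Wilson width | 44.2 |
| Expected Jeffreys width | 39.1 |
| Exact width at non-integer x = 4.95 | 53.4 |
| Wald width with p = 0.99 plugged in: 2 × 1.96 × √(0.99 × 0.01/5) | 17.4 |
| Expected Wald width | 3.5 |

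Only the Wald calculations fall below 19, and Wald is not the method the text names for either planning or analysis.

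**The case against.** The strongest reply is that nothing in the study depends on the 19%. The protocol calls the data preliminary and disclaims powered objectives. No success threshold, stopping rule or sample-size formula uses the figure. Because the final analysis is committed to exact intervals, the reported results will be correct even if this paragraph is not. A cohort of up to five is also defensible for first-in-human feasibility without any precision claim. All of this stands, and it limits the consequence: the error misstates planning precision and leaves the analysis intact.

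Two narrower points also stand. The protocol never says what 0/5 would exclude, so the reading of a 19% bound is a risk of misinterpretation and not something the plan asserts. The source of the 19% is also unknown. It could be a normal-approximation formula at n = 5 (17.4 points), a figure belonging to a design of about 20 subjects (18.4 points), or something else. The text does not settle this, and the finding does not depend on it.

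None of this makes the sentence true. Disclaiming power leaves precision as the only argument offered for n, and that argument rests on a number that the named method cannot produce.

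**Conclusion.** The precision statement is wrong as written and must be corrected. With 5 subjects the expected two-sided 95% exact width is 53.1 points at a 99% or 1% rate, against a stated limit of 19. The minimum over all possible results is 52.2 points. The conclusion rests only on the inputs in Section 8.0, with exact binomial taken as Clopper-Pearson; the alternatives closest to it (mid-P, Wilson, Jeffreys) also fail by a wide margin. The assumed 99% favours the plan: if true success were 85%, the expected width at n = 5 would be 64.2 points.

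The reference to the success rate in the safety example is a separate wording slip with no numerical effect.

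**What to change.** Replace the sample-size paragraph in Section 8.0 with text along these lines:

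> The sample size of up to 5 was chosen for feasibility and not for statistical precision. With 5 subjects, 5/5 successes gives a two-sided 95% exact interval of 47.8% to 100%, and 4/5 gives 28.4% to 99.5%. With 0/5 MACE the interval is 0% to 52.2%. The expected width is about 53 points at an assumed success rate of 99% or an assumed event rate of 1%, and is larger with fewer subjects. Even a perfect result cannot exclude, at the two-sided 95% level, failure or MACE rates of up to about 52%.

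This removes the claim of reasonable precision and makes the safety example refer to the event rate. The existing statement that the study is unpowered and preliminary can stay as it is.

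The cost is one reworded paragraph, with the approval that Section 9.1 requires for any protocol change. No subjects, visits, endpoints or analyses change. The stated precision becomes less favourable, but it will match the intervals the final report will show.

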9.0 Administrative Responsibilities

The GRX with ReMOTE Study will be conducted in accordance with Good Clinical Practice including the study protocol, the fully executed Clinical Study Agreement and all applicable regulations.

9.1 EC Approval

The Clinical Protocol, ICF, and associated documents and any other relevant documentation shall be reviewed and approved by the EC prior to subject enrollment. All proposed changes, including administrative changes, to the protocol, ICF, associated documents and other relevant documentation must be reviewed and approved by Corindus and the EC prior to implementation.

Investigators are responsible for obtaining and maintaining annual renewal of the study by their EC. Evidence of renewal and continued EC approval must be provided to Corindus or their authorized agent prior to continuation of the study at the Investigational Site.

9.2 Confidentiality

All data sent to Corindus or their authorized designee, concerning subjects or their participation in this study will be considered confidential. All data used in the analysis and reporting of this evaluation will be used in a manner without identifiable reference to the subject.

9.3 Study Registration and Publication Policy

The GRX with ReMOTE Study will be registered with clinicaltrials.gov prior to the start of enrollment.

Prior to publication, Corindus will be given the opportunity to review and comment upon any manuscript that contains data derived from this study.

10.0 Supply of Study Materials

10.1 Supply of Investigational Devices

Corindus will ship investigational devices (Local and Remote Control System) only to the qualified investigational site participating in the clinical investigation after Regulatory Authority approval to begin the study and EC approval to begin the study at the site. Corindus will maintain records pertaining to the shipment of the investigational device. Records of shipment include the name and address of the consignee, type and quantity of device, date of shipment and batch or lot number.

10.2 Tracking, Storage and Disposition of Investigational Devices at the Clinical Site

Investigational supplies must be stored in a secure location segregated from standard hospital inventory. The investigational site will maintain complete, and accurate records pertaining to the receipt and disposition of investigational devices, whether used for a study subject, returned to Corindus, destroyed or discarded. The site primary investigator is responsible for ensuring that investigational devices are made available only to site personnel who are authorized to access them and only to subjects under the Investigator's supervision.

APPENDIX A. DEFINITIONS

MACE Definitions

Major Adverse Cardiac Event (MACE): MACE is defined as cardiac death, Q-wave or non-Q-wave myocardial infarction (MI), or clinically driven target vessel revascularization (TVR) by percutaneous or surgical methods.

Cardiac Death: Death due to cardiac causes. If the cause of death cannot be determined, it will be categorized as cardiac.

Myocardial Infarction (Protocol Definition):

Clinically relevant MI after coronary revascularization is defined as:

- Patients with normal baseline cardiac biomarkers
 - CK-MB \geq 10x ULN or cTn (I or T) \geq 70x ULN, or
 - CK-MB \geq 5x ULN or cTn \geq 35x ULN plus new Q-waves in \geq 2 contiguous leads or LBBB
- Patients with elevated baseline cardiac biomarkers
 - Baseline biomarkers are stable or falling:
 - CK-MB \geq 10x ULN or cTn (I or T) \geq 70x ULN of **most recent pre-procedure level**, or
 - CK-MB \geq 5x ULN or cTn \geq 35x ULN of **most recent pre-procedure level** plus new Q-waves in \geq 2 contiguous leads or LBBB
- Baseline biomarkers have not been shown to be stable or falling: CK-MB (or cTn) rises by an absolute increment equal to those recommended above plus new ST-segment elevation or depression plus signs consistent with a clinically relevant MI, such as new onset or worsening heart failure or sustained hypotension.

Target Vessel Revascularization (TVR): Ischemia-driven repeat percutaneous intervention of the target vessel or bypass surgery of the target vessel. A TVR will be considered as ischemia-driven if the target vessel diameter stenosis is \geq 50% and any of the following are present:

- A positive functional study corresponding to the area served by the target vessel.
- Ischemic ECG changes at rest in a distribution consistent with the target vessel.
- Ischemic symptoms referable to the target lesion.

In-Hospital MACE: MACE that occurs within 48 hours of the procedure or prior to hospital discharge, whichever occurs first, in a subject treated with the CorPath GRX System.

Other Definitions

Adverse Event Classification

An adverse event is defined as any adverse change in health or undesirable clinical occurrence from the subject's baseline whether it is considered device related or not.

An adverse event is considered serious if it results in death, is life-threatening, requires hospitalization or prolongation of existing hospitalization, results in persistent or significant disability/incapacity or is an important medical event which may jeopardize the subject and may require medical or surgical intervention to prevent one of the above outcomes.

Procedure-Related Adverse Event

An adverse event is considered to be procedure-related when, in the judgment of the Investigator, it is reasonable to believe that the event is not associated with the CorPath GRX System use. Instead, other products, surgical techniques, or medications required specifically for the procedure are deemed by Investigator as likely to have contributed to the occurrence of the event.

Abrupt Closure: The occurrence of new severely reduced flow (TIMI flow grade 0 or I) within the target vessel that persisted and required rescue by a non-assigned treatment strategy (including emergency surgery) or resulted in MI or death. Abrupt closure requires proven association with a mechanical dissection of the treatment site or instrumented vessel, coronary thrombus or severe spasm. Abrupt closure does not connote "no reflow" (due to microvasculature limitation), in which the epicardial artery is patent but had reduced flow. Abrupt closure also does not connote transient closure with reduced flow in which the index treatment application reversed the closure.

Coronary Dissection - Refers to a split or a tear in the wall of the artery which compresses or compromises the lumen of the artery reducing blood flow.

Coronary Guidewire Dissection - A coronary dissection where a coronary guidewire is inadvertently positioned in a subintimal position or when stiff-tipped or hydrophilic-tipped guidewires are used to cross highly stenosed or totally occluded arteries.

Coronary Perforation - Coronary perforation occurs when a dissection or intimal tear propagates outward sufficient to completely penetrate the arterial wall. This may be caused by pre/post balloon dilatation or post stent deployment where the stent edge causes an edge perforation. Stent edge perforation will range in severity. Ellis classification of coronary perforation:

- Type I - Focal extraluminal crater without extravasation
- Type II - Pericardial or myocardial 'blush' without contrast agent
- Type III - Contrast agent 'jetting' through a frank (>1 mm) perforation

Access Site Complication: A complication occurring at the access site that requires either local intervention or blood transfusion.

Subacute Thrombosis: An abrupt closure of the target vessel that occurs after the index procedure is completed (and the subject has left the catheterization laboratory) and within 48 hours of the PCI.

Threatened Abrupt Closure: A grade B dissection and >50% diameter stenosis or any dissection of grade C or higher.

Bleeding Requiring Transfusion: Any blood loss requiring transfusion of blood products.

Transfusion without clinical evidence of bleeding will be recorded separately.

Coronary Artery Bypass Graft Surgery (CABG): Classified as emergent, urgent, or elective as follows:

- **Elective:** the subject is clinically stable, and the overall medical condition does not indicate the need for revascularization within forty-eight (48) hours.
- **Urgent:** the subject is clinically unstable and the condition warrants revascularization within two (2) to forty-eight (48) hours.
- **Emergent:** the subject is clinically unstable, and the condition requires immediate revascularization within two (2) hours.

Cardiogenic Shock: Subject presents with systolic blood pressure <80 mm Hg for more than thirty (30) minutes unresponsive to fluids or requiring intravenous pressures or an intra-aortic balloon pump.

CK: Creatine kinase, or creatine phosphokinase.

CK-MB: An iso-enzyme of creatine phosphokinase (CK) with a distinct molecular structure specific as an indicator of myocardial cell injury. It is used to evaluate possible causes of chest pain, to detect and diagnose acute MI and re-infarction, and to monitor the severity of myocardial ischemia.

Vascular Injuries:

- **Dissection:** A tear in a vessel allowing blood to enter the wall of the vessel and split its layers. The result is either an intramural hematoma or aneurysmal dilatation.

Dissection classification per National Heart, Lung and Blood Institute:

- Type A: Radiolucent areas within the coronary lumen during contrast injection, with minimal or no persistence of contrast after dye has cleared.
- Type B: Parallel tracts or double lumen separated by a radiolucent area during contrast injection, with minimal or no persistence after dye has cleared.
- Type C: Contrast outside the coronary lumen, with persistence of contrast in the area after dye has cleared.
- Type D: Spiral luminal filling defects frequently with extensive contrast staining of the vessel.
- Type E: New persistent filling defects that may be caused by thrombus.
- Type F: Non-type A-E dissection types that lead to impaired flow or total occlusion of the coronary artery.

No Reflow: Defined as a sustained or transient reduction in antegrade flow that is not associated with an obstructive lesion at the treatment site.

Perforation: Perforations are classified as follows:

- **Angiographic perforation:** Perforation detected by the clinical site at any point during the procedure.
- **Clinical perforation:** Perforation requires additional treatment beyond IV fluid administration (including efforts to seal the perforation or pericardial drainage), or resulting in significant pericardial effusion, abrupt closure, myocardial infarction, or death.

Restenotic Lesion: Defined as lesion in a vessel that had undergone a prior percutaneous treatment.

Thrombus: Discrete, mobile intraluminal filling defect with defined borders with or without staining.

Thrombosis: Academic research Consortium (ARC) definitions:

- **Definite stent thrombosis** requiring the presence of an acute coronary syndrome with angiographic or autopsy evidence of thrombus or occlusion.
- **Probable stent thrombosis** includes unexplained deaths within 30 days after the procedure or acute myocardial infarction involving the target-vessel territory without angiographic confirmation.
- **Possible stent thrombosis** includes all unexplained deaths occurring at least 30 days after the procedure.

TIMI FLOW:

- **TIMI 0:** Dye fails to enter the microvasculature. There is either minimal or no ground glass appearance (“blush”) or opacification of the myocardium in the distribution of the culprit artery indicating lack of tissue level perfusion.
- **TIMI I:** Dye slowly enters but fails to exit the microvasculature. There is the ground glass appearance (“blush”) or opacification of the myocardium in the distribution of the culprit lesion that fails to clear from the microvasculature, and dye staining is present on the next injection (approximately thirty (30) seconds between injections).
- **TIMI II:** There is delayed entry and exit of dye from the microvasculature. There is the ground glass appearance (“blush”) or opacification of the myocardium in the distribution of the culprit lesion that is strongly persistent at the end of the washout phase (i.e. dye is strongly persistent after three (3) cardiac cycles of the washout phase and either does not or only minimally diminishes in intensity during washout).
- **TIMI III:** There is normal entry and exit of dye from the microvasculature. There is the ground glass appearance (“blush”) or opacification of the myocardium in the distribution of the culprit lesion that clears normally and is either gone or only mildly/moderately persistent at the end of the washout phase (i.e. dye is gone or is mild/moderately persistent after three (3) cardiac cycles of the washout phase and noticeably diminishes in intensity during the washout phase), like that in an uninvolved artery. Blush that is of only mild intensity throughout the washout phase but fades minimally is also classified as grade III.

Total Occlusion: True total occlusion is a lesion with TIMI 0 antegrade intraluminal flow and 100% diameter stenosis. A functional total occlusion is a lesion with TIMI 1 antegrade intraluminal flow and 99% diameter stenosis (functional TO) A chronic total occlusion is either of the above that has been present for at least 3 months.

Troponin: a complex of three regulatory proteins, measured levels of which can be used as a test of several different heart disorders, including myocardial infarction.

Unstable Angina: Angina that increases in frequency, intensity, or duration, which occurs at rest, or which is new in onset.

Vessel Characteristics:

- **Angulation:** Vessel angle formed by the centerline through the lumen proximal to the stenosis and extending beyond it, and a second centerline in the straight portion of the artery distal to the stenosis measured in a non-foreshortened view.
- **Spasm:** Transient narrowing >50% diameter in a region where a <25% diameter stenosis had previously been.
- **Tortuosity:** Number of bends that must be traversed by a device to reach the target lesion.
- **Haziness:** Presence of radiolucencies within the arterial lumen not satisfying the criteria for thrombosis.

Lesion Characteristics:

- **Anastomotic:** Lesion located at the junction of a bypass graft and native vessel.
- **Aneurysm:** An expansion of the lumen in the region of maximum stenosis that extends with a wide or narrow mouth beyond the apparent normal contour.
- **Aorto-ostial:** A lesion is classified as aorto-ostial when it is located within 3 mm of the origin of the coronary vessels from the aorta.
- **Bifurcation:** Lesion located at the origin, immediately after, or branch that has a diameter $\geq 2\text{mm}$.
- **Eccentricity:** A stenosis that has one of its luminal edges in the outer one-quarter of the apparent normal lumen.

- **Calcification:** Readily apparent densities noted within the apparent vascular wall at the site of the stenosis. Calcification is classified as none/mild, moderate when densities noted only during the cardiac cycle prior to contrast injection, and severe when densities noted without cardiac motion prior to contrast injection generally involving both sides of the arterial wall.
- **Intimal Flap:** Extrusion of tissue extending from the arterial surface into the lumen.
- **Irregularity:** Lesion borders with abnormal margins based on the presence of an ulceration, aneurysm, or intimal flap.
- **Length:** “Shoulder to shoulder” distance, which is measured from the proximal shoulder to the distal shoulder of a lesion in the projection that shows the most elongated view of the stenosis.
- **Discrete:** Lesion length <10.0 mm.
- **Tubular/Focal:** Lesion length \geq 10.0 mm and \leq 20.0 mm.
- **Diffuse:** Lesion length \geq 20.0 mm.
- **Location:** Designated as ostial, proximal, mid and distal.
- **Ostial:** Lesions that begin within 3.0 mm of the origin of the artery.
- **Ulceration:** A small crater or flap in a lesion.

ACC/AHA Lesion Characteristics (Type A, B and C):

- **Type A Lesions (high success, >85%; low risk):** Discrete (<10mm length), concentric, readily accessible, non-angulated segment, 45° smooth contour, little or no calcification, less than totally occlusive, non-ostial in location, no major branch involvement and absence of thrombus.
- **Type B (B1 and B2) Lesions (moderate success, 60 - 85%; moderate risk):** Tubular (10-20 mm length), eccentric, moderate tortuosity of proximal segment, moderately angulated, $45 - 90^{\circ}$ irregular contour, moderate or heavy calcification, ostial in location, bifurcation lesions requiring double guidewires, some thrombus present and total occlusion < 3 months old. Type B2 lesion classification has more than one characteristic above.

- *Type C Lesions (low success, < 60%; high risk):* Diffuse (>2 cm length), excessive tortuosity of proximal segment, extremely angulated, > 90°, inability to protect major side branch, degenerated vein grafts with friable lesions and total occlusions > 3 months old.

Procedure Title: CorPath GRX with Remote Study	
Doc Number: 104-07972	
Revision: A	Page: 38 of 39

